**13.0 Withdrawal of Subjects**

The PI may withdraw a participant from the study at any time if they decide it is in their best interest, if they do not follow the investigator's instructions, or if they fail to keep study visits. This may also occur if there is a protocol violation or early closure of the study.

**14.0 Risks to Subjects**

We do not anticipate any significant risks related to the completion of this study. However, as with any research study there is a risk of disclosure of information that can lead to a loss of confidentiality. As well as having a comprehensive plan that details data safety, handling, monitoring, storage and security procedures, we will further minimize the potential for loss of confidentiality through the physical separation of participant names from their research record.

Additionally, it is possible that a participant might experience some emotional distress while responding to the survey questions or participating in key informant interviews. If this were to occur, the participant would be referred to a psychologist or psychiatrist for counseling. Reactions will be monitored by the PI (who will be conducting the key informant interviews) and signs of significant distress will be followed-up to identify any serious psychological problems. In the rare and unexpected event of serious or life threatening level of distress, a psychologist or psychiatrist will be contacted as well as the participant's primary care provider of record.

The PROMIS Emotional Distress: Depressive Symptoms Instrument will be administered to young adult, adolescent and caregiver participants at baseline, 6-weeks, 12-weeks, and 3-months

post-intervention. The REDCap database will be developed with scoring to allow study personnel to immediately view scores, including a raw score, t-score, and response pattern scoring. If any of the following criteria are met, the participant will be asked if they would like assistance with obtaining mental health resources:

- t-score for depression is one standard deviation above the mean (60) for the general population (44), or above
- t-score demonstrates a minimally important difference (3.0 – 4.5) from previous assessment (45)

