## 10.0 Study Design / Methods

This single-group study will assess feasibility to test reach, efficacy, adoption, implementation, and maintenance of SMYLS using the RE-AIM framework (25) (Table 1) with 30 adolescents (A)/caregivers (CG), 15 young adults, and 5 healthcare providers involved with their care. YA and A/CG will be enrolled for a total of 6 months (12-week intervention with 3-month follow-up). Providers will be enrolled for as long as an adolescent under their care is currently enrolled ( $\geq 6$  months). We will obtain outcomes data on feasibility, self-management behaviors, and healthcare activities (primary aim), and transition readiness, symptoms, quality of life, and healthcare utilization (secondary aim). Measures include patient report via surveys, data recorded via the app, such as symptoms and app use, communication content from MyChart messaging, and in-depth data via key informant interviews.

Table 1 outlines the data to be collected and survey instruments to be administered at each of four data collection points: baseline, 6-weeks (mid intervention), 12-weeks (end of intervention), and 3-months post-intervention. Participants will be given the option of completing surveys in one of three ways: in person in a private room at the MUSC Pediatric Sickle Cell Clinic, by phone, or electronically through a link to REDCap. Estimated time for completion of surveys at each of the 4 visits is approximately 45 minutes. For in-person and phone data collection methods, all data will be recorded in REDCap by the PI or IRB-approved study personnel. Reimbursement to young adult and adolescent/caregiver dyads will be \$50 in the form of a gift card presented at each of the 4 data collection points. For A/CG participants, payments will be given to the caregiver; in the case of phone or electronic data collection, participants will be mailed the gift card by certified mail or will receive an electronic gift card via email.

Healthcare providers will complete a demographic survey in person or electronically at baseline. Subsequently, no surveys will be administered to healthcare providers.

Healthcare providers' study activities involve communicating with the young adults and adolescents/caregivers via MyChart.

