**Post-intervention interviews:** Post-intervention interviews will be conducted by phone or in person (according to participant preference) with up to 15 adolescent/caregiver dyads and with up to 15 young adult participants to obtain more in-depth data on accessibility, usability, adherence to the intervention, and to explore how self-management behavior development influenced healthcare decision-making, such as actions taken to prevent pain. Participants who have completed the 12-week intervention period will be asked if they are interested in participating in an interview. We will use a purposeful sampling strategy to identify up to 15 dyads for interviews and will ask all young adult participants if they are interested in participating in an interview. Semi-structured interviews will be conducted using a qualitative descriptive approach, will last approximately 45 – 60 minutes, and will be conducted according to an interview guide with open-ended questions and prompts. The interviews will be audio recorded and transcribed by an outside agency with which MUSC has established a BAA for subsequent review and analysis. Dyads participating in key informant interviews will be compensated with a \$50 gift card.

In addition to conducting interviews with young adults and dyads, we will also conduct key informant interviews with up to 5 healthcare providers in person or by phone. Similarly to interviews with young adults and dyads, interviews with providers will be conducted to obtain more in-depth data on accessibility, usability, and adherence to the intervention. Semi-structured interviews will be conducted using a qualitative descriptive approach, will last approximately 45- 60 minutes, and will be conducted according to an interview guide with open-ended questions and prompts. Interviews will be audio recorded and transcribed by an outside agency with which MUSC has established a BAA

for subsequent review and analysis. Providers participating in key informant interviews will be compensated with a \$50 gift card.

Table 1: Measurement Framework

\*A = adolescents, CG = caregivers, HCP = healthcare providers

	Measures/instruments (number of items; Cronbach's alpha)	Sources	Time points
Demographic and clinical characteristics	Demographic survey	YA, A/CG report HCP report	Baseline
RE-AIM			

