Reach: (primary aim) Sample Recruitment	Electronic log of sample characteristics; recruitment and enrollment activities	Recruitment tracking tools	Ongoing
Efficacy: Self-management outcomes (primary aim): Monitoring and tracking symptoms Attending clinic appointments Administering home medications and treatments Symptoms and health-related outcomes (secondary aim): Healthcare utilization (A only) Transition Readiness (A only) Pain (A only) Fatigue (A/CG) Depression (A/CG) Anxiety (A/CG) Sleep Interference (A/CG) Self-Efficacy (A/CG) Quality of Life (A/CG)	Pain and other symptom recording; treatments recorded; utilization reports 
 
PROMIS Pain Interference : Adult/Peds/parent proxy (8;0.87) (26)
 
PROMIS Fatigue SF : Adult (4; >0.9)(27); Peds/parent proxy (10 ; 0.87)(28)
 
PROMIS Emotional Distress: Depressive Symptoms SF : Adult (4; 0.97) (29); Peds/parent proxy (8; 0.94)(30)
 
PROMIS Emotional Distress: Anxiety SF Adult (4;0.97) (31); Peds/parent proxy (8; 0.83) (26)
 
PROMIS Self-Efficacy including general, manage daily activities, manage meds/treatment, manage symptoms: Adult (16; 0.97) (32)
 
Sickle Cell Self Efficacy Scale (9)
 
PROMIS Sleep Disturbance: Adult (4; 0.88)(33)
 
Adolescent Sleep Wake Scale (28; 0.86) (34)
 
Peds QL with Sickle Cell Disease Module (43; 0.95) (35)
 
Adult Sickle Cell Quality of Life Measurement Information System (30)
 
PROMIS Global Health Adult (10)
 
STARx (18; 0.8) (36)
 
Youth and Parent Sickle Cell Responsibility Scale
 
	YA, A/CG report Web-based application data capture Semi-structured interview Quality checks	Baseline, 6 weeks, 12 weeks, 3-months post intervention Ongoing Weekly
Adoption: (primary aim) Adherence (A/CG, HCP) Acceptability (A/CG, HCP) Education (A/CG) Symptom monitoring and tracking (A/CG) Communication (A/CG, HCP)	App overall use data; app component use data; satisfaction; reported problems; YA, A/CG-provider message content; MAUQ_SPA	Web-based application data capture Semi-structured interview Quality checks	Post intervention Ongoing Weekly

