## 11.0 Data Management

**Sex as a biological variable.** We recruit equal numbers of male and female adolescents and preliminarily explore for differences by sex in outcomes, such as acceptability, satisfaction, communication content, symptoms, quality of life, transition readiness, and utilization by conducting preliminary subgroup analyses in preparation for the subsequent larger trial.

**Feasibility processes.** Variables will include those pertaining to study procedures as well as participant variables. Specifically, 95% confidence intervals for proportions will be used to estimate dichotomous outcomes including the proportion of YA, A/CG who agree to participate out of the number approached, the proportion adherent to the intervention protocol, i.e., providing daily symptom monitoring/tracking, using the education component, responding to messaging, lost to follow up, etc. For the continuous feasibility measures (length of time spent in app components), frequency distributions and the median and mean responses with 95% confidence intervals will be obtained. Benchmarks for feasibility success are recruitment rate of at least 2 YA or A/CG per week, retention rates of 70%, use of at least one component of the app  $\geq 2$  days per week (adherence), and expressed satisfaction in key informant interviews (37).

**Outcome measures and estimates of variability.** Secondary aim outcomes variables will include measures of symptoms (pain, fatigue, depression, anxiety, sleep interference), quality of life, transition readiness, and utilization (number of appointments kept, number of ED visits). Demographic and clinical variables obtained at baseline will be described via measures of central tendency (mean, median), variability and frequency distributions as appropriate. Additionally, demographic and clinical characteristics for those who adhered to the study protocol versus those who did not adhere (non-adherers and drop outs) will be compared to better describe the study population. For continuous quality of life measures, the difference between pre-and post-intervention measurements will be estimated via 95% confidence intervals. To assess preliminary intervention effects, we will conduct repeated measures ANCOVA with variables in individual models adjusting for “dose” defined as number of times each portion of the app was accessed, total time spent in each portion of the app, number of days symptoms were recorded, and number of A/CG-provider messages.

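### The depression change criterion gives a range and no direction, and it looks back only to the previous form, so below a t-score of 60 an offer of help can be inconsistent or missed (minor)

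*Combined protocol and SAP*

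**What the plan says.** Section 14.0 has young adults, adolescents and caregivers complete the PROMIS depression form at all four visits, which Section 10.0 gives as "baseline, 6-weeks (mid intervention), 12-weeks (end of intervention), and 3-months post-intervention". If either of two criteria is met, "the participant will be asked if they would like assistance with obtaining mental health resources".

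- First criterion: "t-score for depression is one standard deviation above the mean (60) for the general population (44), or above".
- Second criterion: "t-score demonstrates a minimally important difference (3.0 – 4.5) from previous assessment".

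The database is to be built so that staff are able "to immediately view scores, including a raw score, t-score, and response pattern scoring". A change score is not named in that list.

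Table 1 in Section 10.0 lists the instrument ("PROMIS Emotional Distress: Depressive Symptoms SF") with its "number of items; Cronbach's alpha": 4 items and 0.97 for the adult form, 8 items and 0.94 for the pediatric and parent-proxy form. Neither Table 1 nor any other section available for review says more about how the change criterion is to be applied.

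**The concern.** Either criterion is enough, so for anyone below 60 the second is the only score-based route to the offer. It applies at the three follow-up visits, since baseline has no earlier form. It has two separate weaknesses.

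- **It does not give one answer.** A minimally important difference quoted as a range suits interpretation, but a trigger needs one number. The text also does not say that only worsening counts. Two staff members could see the same pair of scores, and one could make the offer while the other does not.
- **It has no memory beyond one visit.** This part of the wording is clear. The result is a gap in sensitivity: a participant can worsen in small steps by more than the sponsor's own important difference and never be asked.

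At stake is who is asked a question about mental health resources, in a group that includes minors aged 11 to 17.

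**Working it through.** **The plan's own figure.** On the usual t-score scale (mean 50, SD 10; a convention the protocol does not print), one SD above the mean is 50 + 10 = 60, which matches the first criterion. The range 3.0 to 4.5 comes from a cited source and cannot be re-derived from the documents.

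**Score pairs below 60 (no assumptions needed)**

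| Scores | Change | Rise ≥ 3.0 | Rise ≥ 4.5 | Either direction ≥ 3.0 |
|---|---|---|---|---|
| 50 to 53.5 | +3.5 | offer | none | offer |
| 50 to 59 | +9 | offer | offer | offer |
| 55 to 51 | −4 | none | none | offer |
| 50, 52.9, 55.8, 58.7 | +2.9 each, +8.7 in all | none | none | none |

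The first row shows the ambiguity and the last row the gap. With 4.5 as the cut-off, unflagged drift can approach 3 × 4.4 = 13.2 points. That is a limiting case, because staying below 60 then requires a baseline below 60 − 13.2 = 46.8.

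**Forms concerned.** (30 adolescents + 30 caregivers + 15 young adults) × 3 follow-ups = 225. At the 70% retention benchmark in Section 11.0, 225 × 0.70 = 157.5, about 158.

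**Flags from measurement error alone.** Assumptions: SD 10, the Table 1 alphas used as reliability, independent normal errors, no true change.

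- Standard error of measurement = 10 × √(1 − alpha): adult 1.73, pediatric 2.45.
- SD of a difference d between two forms = that × √2: adult 2.45, pediatric 3.46.
- P(d ≥ 3.0) = 0.110 adult, 0.193 pediatric.
- P(d ≥ 4.5) = 0.033 adult, 0.097 pediatric.

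Table 1 does not settle which form caregivers complete, so both cases are shown. Counts include forms already at 60 or above.

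| Expected flags over 225 forms | Rise ≥ 3.0 | Rise ≥ 4.5 | Ratio |
|---|---|---|---|
| Caregivers on adult form (135 adult, 90 pediatric) | 32.3 | 13.2 | 2.4 |
| Caregivers on proxy form (45 adult, 180 pediatric/proxy) | 39.7 | 18.9 | 2.1 |

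**Allowing ordinary variation between visits.** Simulation of four visits, SD 10, mean 50 or 55, between-visit correlation 0.6 to 0.9 (all assumed), counting only follow-up forms below 60. A rise of at least 3.0 flags 21% to 32% of forms and a rise of at least 4.5 flags 13% to 26%. Within each setting the ratio is 1.2 to 1.7. At mean 50 and correlation 0.8 the shares are 28% and 21%.

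**Size of the gap.**

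- In the same simulation, take people who never reach 60 and end at least 4.5 above baseline. The previous-form rule misses about 1% to 4% of them at 3.0 and about 4% to 22% at 4.5.
- A deliberately hard case is a true rise of 2 points per interval from 50, with the measurement error above. The chance of never being asked is:

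| Form and cut-off | Previous form only | Previous form or baseline |
|---|---|---|
| Adult, 3.0 | 19% | 5% |
| Adult, 4.5 | 57% | 19% |
| Pediatric, 3.0 | 13% | 6% |
| Pediatric, 4.5 | 38% | 18% |

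**Extra flags from adding baseline, error only.** The first follow-up is unchanged, because there the previous form is the baseline form.

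- At 3.0: 45.5 − 32.3 = 13.2 (caregivers on adult form), or 55.2 − 39.8 = 15.4 (proxy form).
- At 4.5: 19.5 − 13.2 = 6.3, or 27.6 − 18.9 = 8.7.

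**The case against.** The case for leaving the text alone is a fair one.

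- **Context supplies the direction.** The criterion leads to an offer of mental health resources, so staff would almost certainly read it as worsening. This stands, and it limits the size of the point. A reader might set any change of 3.0 or more, improvements included (about 65 to 79 of 225 forms), against a rise of 4.5 or more (13 to 19 forms) and infer that the reading changes the count 4- to 5-fold. That contrast rests on an unlikely reading. Between the two plausible readings the factor is 1.2 to 2.4. Direction settled by context still leaves 3.0 against 4.5 open.
- **The reference form is not ambiguous.** This also stands. A reader might treat the previous-form reference as a third unclear element; it is plainly stated, and the criticism is only that it misses cumulative worsening. The 2-points-per-interval illustration is built to slip under both cut-offs. If the same 6 points come in the first or last interval, the chance of never being asked falls to 6% to 8% at 3.0 and 23% to 24% at 4.5.
- **Alpha is internal consistency, not stability between visits.** This is correct, so the error-only counts are illustrative.
- **The REDCap list is not exhaustive,** and subtracting two scores is easy. Also correct; the missing change score is a convenience, not a defect.
- **Other protections exist.** Section 14.0 provides for referral when distress arises during surveys or interviews, and the monitoring plan has weekly contact with participants. A reader might infer that a crisis would go unanswered, or that no one is responsible for acting on scores. The documents do not support either. These provisions do not, however, settle what the score criterion means.

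**Conclusion.** The point holds as a minor one. The second criterion cannot be applied in one way as written, because for scores below 60 a rise of at least 3.0 but under 4.5 has no settled answer. As a separate matter, it never flags a series of sub-threshold rises, even when their total exceeds the sponsor's own important difference. Both conclusions follow from the text and the example scores alone.

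The size rests on assumptions. The choice between 3.0 and 4.5 changes the number of offers about 2.1- to 2.4-fold if all change is measurement error, and about 1.2- to 1.7-fold under ordinary variation between visits. The consequence is confined to who is asked about resources. This is a single-group feasibility study classed as minimum risk, and no aim, endpoint or estimate depends on the rule. The trigger at 60 or above and the distress referral work under any reading.

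**What to change.** Replace the second criterion in Section 14.0 with: *a rise (worsening) of 3.0 points or more in t-score from the last completed assessment or from baseline.* The value 3.0 is the lower bound of the sponsor's range and the protective choice. The sponsor may set 4.5 instead if fewer offers prompted by measurement error are preferred, but one number should be named. Add the two changes (from the last form and from baseline) as calculated fields in the REDCap scoring already planned.

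The cost is a short amendment, two fields and some additional offers. Under the error-only assumptions and 225 forms, the baseline comparison adds about 13 to 15 offers at 3.0, or about 6 to 9 at 4.5. Before that addition, choosing 3.0 over 4.5 accounts for about 19 to 21 offers (32.3 − 13.2 = 19.1; 39.7 − 18.9 = 20.8). Each is a single question to the participant. No new notification or review procedure is needed for this point.

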## 15.0 Potential Benefits to Subjects or Others

If a participant agrees to take part in this study, there will be no direct medical benefit to them. We hope the information learned from this study will aid patients and clinicians in the future. The data collected from this study will not directly affect the treatment being given to the patients. The risks associated with the proposed study are minimal and include psychological and physical strains that might be encountered in everyday life. The benefits of the study outweigh the risks. We anticipate this study will lead to improved self-management of SCD through the use of mobile health technology. As such, the resulting information would be used to develop self-management strategies among young adults and adolescents with SCD and their families moving forward.

